Study of Naltrexone-Induced Blockade of Antidepressant Effects

[name], PhD

Assistant Professor of Psychiatry

[name]

University of Pittsburgh [contact]

Email: [contact]

Clinical trial number (clinicaltrials.gov): NCT04322526

Date: March 30th, 2020.

Placebo Effects in Major Depression: A pharmaco-fMRI Intervention

INTRODUCTION:

This NARSAD Young Investigator Award application proposes to define the neural and molecular bases of placebo effects in Major Depression. This proposal would be a perfect extension to my on-going study aimed at developing and piloting a functional magnetic resonance imaging (fMRI) task to investigate the neural signature of placebo effects in Major Depression, which will be used in this application. This study would also be an ideal add-on to a current clinical trial at [name] laboratory investigating the role of opioid and cannabinoid interactions in placebo effects in depression. These results will provide robust preliminary data, to inform the design of a randomized controlled trial (RCT) that would use imaging-based biomarkers of placebo effects, to be submitted as an R01 application to the National Institute of Mental Health.

BACKGROUND & STUDY GOAL:

The placebo effect – a positive psychophysiological response attributed to inert treatments – is an important yet seemingly misunderstood phenomenon in conventional medical science. While placebo effects are as old as healing itself, it is still unknown why certain diseases, such as depression, show remarkably and increasingly high placebo rates (Walsh et al., 2002), hindering the development of novel therapeutics and predictors of treatment response. In RCTs of antidepressants for adults, response rate to placebo ranges from 25-60%, compared to 50% response rate to antidepressant medication (Quitkin, 1999). The failure to differentiate between placebo and antidepressant responses has caused large pharmaceutical companies to reduce or discontinue research focused on treatments for depression and other mental illnesses (Cressey, 2011). Furthermore, only one landmark published study has investigated the neural correlates of placebo effects in depression (Mayberg et al., 2002). Therefore, there is a critical need to define biomarkers of placebo effects in depression and translate this knowledge into novel marker-informed clinical trial designs.

Preliminary studies: Neuroimaging offers a precise and objective way to characterize the neural and molecular basis of the placebo response in humans. We have already established the utility of positron emission tomography (PET) with the μ -opioid selective ligand [^{11}C] carfentanil to investigate the neurobiology of placebo effects using a pain model [for a review, (Pecina and [name], 2014)]. Additionally, we have used the same methodology to define the neural bases of placebo effects in patients with Major Depressive Disorder (MDD) (PI: [name]). This study demonstrated that improvement of depressive symptoms in response to placebo administration was positively correlated with placebo-induced opioid release in the medial thalamus, anterior cingulate cortex (ACC), nucleus accumbens, and amygdala. These data show that placebo administration in patients with MDD is associated with increased opioid neurotransmission in regions implicated in emotion regulation. More recently, I have developed and piloted an fMRI experiment to characterize the cognitive mechanisms involved in placebo effects in patients with MDD. This fMRI task is specifically designed to record and modulate mood improvement by providing simulated neurofeedback in the context of an intravenous placebo administration with expectations of fast-acting antidepressant effects. In a pilot study using this task, patients with MDD who reported acute mood improvement in response to simulated positive neurofeedback showed increased blood oxygen level dependent (BOLD) responses in the ACC (Fig.

[figure not shown]

Fig. 1: Responses to the Simulated Real-time Neurofeedback fMRI task.
Simulated positive neurofeedback during this task resulted in 1) Acute mood improvement ($t=-2.8$, $p=0.03$) (left), and 2) Increased BOLD response in the rostral ACC (and also the dorsal and subgenual ACC) in placebo responders ($n=3$) compared to non-responders ($n=3$) (right).

intravenous antidepressant", which will be either naloxone (NARCAN® injection, naloxone hcl injection. Endo Pharmaceuticals, Inc.) or saline (0.9% Sodium Chloride Injection). As previously described (Sprenger et al., 2011), naloxone will be administered in bolus of 0.15 mg naloxone per kg bodyweight or the same amount of saline, fifteen minutes before the experiment (Fig. 2). Because of the relatively short half-life of naloxone, an additional constant intravenous infusion (dose of 0.2 mg/kg/h or saline for the duration of the fMRI experiment) will be administered. To control for the effects of naloxone on blood pressure, the participants' blood pressure will be determined directly before and 5 minutes after drug application and at the end of the experiment.

Inside of the scanner, participants will undergo the "Simulated Real-Time Neurofeedback" fMRI task (Fig.2), which consist of periods of anticipation of "drug" or "drug-free" infusion (10s), followed by periods of simulated positive or negative neurofeedback (16s). Before the experiment, patients will be trained to expect positive neurofeedback and acute mood improvement in response to each "drug" infusion and negative neurofeedback and acute mood-worsening in response to each "drug-free" infusion trial. The experiment will consist of six 7-minute runs of 12 trials counterbalanced within and between runs. After the experiment, we will assess the task's credibility and patients who did not believe the experiment will be excluded from the study. All newly collected fMRI data will be analyzed using standard procedures (Ashburner, 2007). At the group-level, a random effects analysis will determine the main effects of the valance (positive versus negative neurofeedback) resulting in statistical parametric maps (t or F statistics), which will be thresholded with height and extent values generated by Monte Carlo simulations with 3dClustSim to protect against overall type I error at $p < 0.05$. To control for potential confounders, sex and depression severity will be entered as covariates in statistical models. The whole-brain analyses will be complemented by hypothesis-driven analyses in the rACC. Average BOLD signal within the rACC will be extracted and regressed against variables of interest.

Expected Outcomes and Impact: First, we expect to demonstrate that naloxone will reverse the acute mood improvement and increased rACC BOLD activity induced by positive neurofeedback with expectations of mood improvement (AIM 1). Second, we expect to demonstrate that increased rACC BOLD activity induced by positive neurofeedback will be associated with greater acute mood improvement (AIM 2). Third, we expect to demonstrate that rACC BOLD activity induced by positive neurofeedback mediates the effect of group (naloxone versus saline) on acute mood improvement (AIM 3). The results from this study are expected to have an important impact on our ability to understand the neurobiology of placebo effects in Major Depression, to detect novel target for drug development and to develop imaging-based biomarkers of placebo effects.

Research design: We will recruit 20 un-medicated patients with Major Depression aged 18–55 years with a current moderate-to-severe first depressive episode (Hamilton Depression Rating Scale scores >14). We will use authorized deception (Miller et al., 2005) to inform patients that the purpose of the study is to investigate the effects of a fast-acting intravenous antidepressant treatment on real-time brain signal as well as to assess the test-retest reliability of this procedure (this is to justify a second experiment). After assessing eligibility, patients will receive continuous infusion of the "fast-acting

Figure 1. Study design and contextual framing fMRI task.

Participants underwent a randomized, double-blind, placebo-controlled, cross-over study of one dose of oral 50mg naltrexone hydrochloride (ReVia® [package insert]. Toronto, ON: Teva Canada Limited; 2015) (onset of action: ≥ 15 minutes; peak effect: ~ 1 hour; duration: ~ 24 hours) or matching placebo (Figure 1A). The two sessions occurred within 7-10 days from one another. Naltrexone or placebo pills were ingested 60 minutes before the fMRI scanning session. Participants were informed that the purpose of the study was to investigate the effects of opioid blockade on emotional processing. They were also informed about naltrexone, including its pharmacological properties, its general clinical use, and its possible side effects. However, they were not informed about the potential effects of context.

Of the 25 enrolled participants who received the naltrexone/placebo pill, two dropped out prior to scanning – one who was claustrophobic and another who had a positive pregnancy test. We excluded three additional participants who did not complete their placebo session. The final sample size for the contextual framing task was 20 for the placebo session, and 17 for the naltrexone session (thee participants did not complete the fMRI session naltrexone session, but their results from their placebo session were still included in the analysis). The final sample size for the antidepressant placebo fMRI task was 20 for both sessions.

Contextual Framing fMRI Task

The contextual framing task (Figure 1B) was iteratively refined as a simpler version of a similar task utilized by Mobbs and colleagues [39]. In this mixed block/event-related design, participants saw an emotionally evocative/salient contextual image for 2 seconds (Context phase) followed by the rating of the valence of an ambiguous emotional expression for 3 seconds (Emotion & Rating). The jittered inter-trial interval was ~ 3 seconds (2-6s range, S.D.=1.1)].

For the contextual images, we used a total of 72 emotionally evocative color photographs (36 pleasant and unpleasant images) from the International Affective Picture System (IAPS) database [44], which contains normalized scores of valences (pleasant = 9, unpleasant =1) and arousal (high = 9, low = 1) for all the images. Based on these scores, we selected 72 contextual images with high or low valence scores (pleasant > 7.3 and unpleasant < 3.4) and moderate arousal score (less than 6) to avoid excessively salient stimuli. This normalized image set provided the image-context for influencing the rating of ambiguous faces.

We then generated three types of emotional faces with ambiguous expressions from the NIM-STIM database (<http://www.macbrain.org/resources.htm>). First, we selected images of 48 individuals' faces that had a neutral facial expression. Then, the neutral face image was morphed with the same individuals' face image with a happy or fearful expression to generate ambiguous faces using a face-morphing software (Fantamorph 2.5). To maintain the ambiguity of facial expression, we merged morphed only 20% of happy or fearful face to with the neutral face.

Prior to the fMRI scan, participants received the following instructions: "You have two choices for rating each face: + (positive), indicating that the person seems happy, pleased, or delighted; or - (negative), indicating that the person seems sad, afraid, angry, or disgusted. You will see faces only for a brief moment, so please respond as fast as possible. The pictures of faces will alternate with other kinds of pictures." To avoid participants' guessing the premise of the task, we added the following instruction: "Pay attention to these non-face pictures because you'll be asked about them afterwards. But remember that your main task is to rate the facial expressions." Participants reported their responses by clicking either the left or right index finger one of the buttons of the 5-button response box in each hand. They were instructed to rate the facial expression by pressing a right index finger to select positive ("+") or a left index figure to select negative ("−") during the first run and the opposite during the second run.

Participants completed 144 trials (72 trials with each unique context picture, repeated twice) for each visit (Placebo and Naltrexone session). The task lasted approximately 20 minutes. Three types of ambiguous faces appeared equal times, and the sex of the face was randomized. The trial orders were optimized by using the easy-optimize-x tool that was implemented in MATLAB [45].

Antidepressant Placebo fMRI Task (See figure 2 in study protocol).

Participants were informed that the purpose of the study was to investigate the neural effects of a "fast-acting antidepressant" compared to a "conventional antidepressant". In addition, participants were told that the experimental procedures consisted in the administration of multiple antidepressant infusions during an fMRI scanning session where we recorded their brain activity, which we called neurofeedback.

Before entering into the scanner, a certified nurse placed an fMRI intravenous compatible line in the participant's arm for the "antidepressant" infusions. In addition, patients watched a fragment of the task to be displayed inside of the scanner and were informed that the positive neurofeedback signal (higher tracing) reflected the effectiveness of the drug infusion and might result in mood improvement during the experimental session, whereas the baseline neurofeedback signal was unlikely to cause mood improvement. Once in the scanner, an MRI compatible pump, controlled from outside the scanning room by pushing the "go" trigger, delivered the saline to the participant during the scanning session. The infusion was manually started at a given flow rate and volume, at the beginning of each run.

Then, participants completed the Antidepressant Placebo fMRI Task, which features two putative components of the placebo effect: the expectancy and reinforcement condition, each followed by an expectancy and mood rating cue, respectively. The expectancy condition involves two "antidepressant" infusion cues – described as a "fast-acting" and a "conventional antidepressant" – and two no-infusion cues – described as periods of equipment calibration. During the "antidepressant" infusion cue (4s), a bar is filled at four 1s-periods

representing 0%, 33%, 66% and 100% of the dose administered. During the calibration no-infusion cue (4s) the bar remains empty. For the reinforcement condition (10s) we used sham neurofeedback as a secondary reinforcer of the “antidepressant” effects. In the high-reinforcement condition sham neurofeedback is positive 88% of the trials (vs. 12% baseline). In the low-reinforcement condition, sham neurofeedback is positive 25% of the trials (vs. 75% baseline). Participants rated their expected and actual change in mood (YES/NO) in response to each infusion/neurofeedback signal respectively by using a keypad and their index fingers.

The combination of the expectancy and reinforcement manipulation results in 4 different conditions: 1) Infusion cue + High reinforcement, 2) Infusion cue + Low reinforcement, 3) Calibration cue + High Reinforcement and 4) Calibration cue + Low Reinforcement. Each condition is color coded as red, blue, yellow and green respectively (Fig.1). Random jitters were included between trials and between the expectancy and the reinforcement manipulation. The jitter duration was randomly selected from an exponential distribution bounded between 0.33 and 2 s. One jitter length was sampled from the uniform distribution with bounds 4-6 s to increase randomness.

MRI Data Acquisition

Structural and functional MR images were collected at the University of Pittsburgh Magnetic Resonance Imaging Center on a 32-channel parallel receive-transmit head coil on a 3T Siemens PRISMA scanner (Munich, Germany). All scanning was conducted in the afternoon ~ 1h after receiving either placebo or naltrexone. A sagittal, whole brain 3D magnetization prepared rapid gradient echo (MPRAGE) with repetition time (TR)=2400ms, echo time (TE)=2.22ms, flip angle (FA)=8deg, inversion time (TI)=1000ms, field of view (FOV)=300x320, 208 slices, 0.8mm isotropic (0.4mm space between slices), with Generalized Autocalibrating Partial Parallel Acquisition (GRAPPA) factor of 2, and lasted ~6min 38 sec. An axial, whole brain (including cerebellum and brainstem) echo planar (EPI) T2*-weighted functional images were collected to measure the blood oxygen-level dependent (BOLD) response with TR=1000ms, TE=30ms, FA=45°, FOV=95x95, 60 slices, 2.3mm isotropic (no spaces), multiband factor of 5, and 1200 volumes (two 10-minute runs). Participants were scanned for 90 minutes and this task started at approximately minute 65.

MRI Preprocessing

Acquired images were preprocessed using functions in the following software packages: NiPy [46], AFNI [47], BrainWavelet Toolbox [48] and the fMRI software library (FSL, [49]). We have previously detailed this preprocessing pipeline elsewhere [50]. Specific methods and programs used were outlined below.

Anatomical images first underwent gradient unwarping, and then were registered to the MNI152 template using both affine and nonlinear transformations methods implemented in FLIRT (FSL) and FNIRT (FSL), respectively. A mask of the brain was also created by removing the non-brain voxels from the anatomical images using BET (FSL) for later use in functional image co-registration.

The functional images underwent slice timing and motion correction simultaneously using NiPy’s four-dimensional registration algorithm SpaceTimeRealign. Running both simultaneously ensured that motion artifacts would not be reintroduced into the data in later processing. Non-brain voxels in the images were removed by masking low intensity voxels, calculated from the field map, and using brain extraction function BET (FSL). After intensity-normalizing every voxel to have a mean of 1000, wavelet despiking was performed using the BrainWavelet Toolbox with the spike threshold set to 10. The resulting image was aligned and warped to their anatomical images, resampled to 3mm isotropic voxels, and warped into MNI152 standard space. A 7mm full-width at half maximum kernel was used to smooth the images spatially and a high-pass filter was applied to remove signal slower than 0.008 Hz. Lastly, the images were intensity normalized by rescaling the intensity by 100 divided by voxel mean.

MRI Analysis

MRI First Level Analysis of the Contextual Framing Task. We constructed regressors for emotion and context type, and their interaction terms. The emotion regressor was coded as one 1, for happy faces, 0 for neutral faces, and -1 for fearful faces. Similarly, the context regressor was coded as 1 for pleasant and -1 for unpleasant context. The interaction term included two regressors, one for the effect of context on happy faces (1 for pleasant context/happy faces, -1 for unpleasant context/happy faces, 0 for the remaining conditions), and

another one for the effect of context on fearful faces (1 for pleasant context/fearful faces, -1 for unpleasant context/fearful faces, 0 for the remaining condition). We also included a trial regressor of no interest.

We aligned the boxcar regressors with trial onset (length = trial duration) and convolved them with the hemodynamic response function. We then used the resulting time-series to regress against BOLD signal for each run and participant, and constructed contrasts for each regressor (i.e., emotion, context type, emotion x context type interaction).

MRI First Level Analysis of the Antidepressant Placebo fMRI Task: We constructed four event regressors: infusion event, expectancy ratings event, neurofeedback event and mood ratings event. We constructed two additional regressors for the expectancy manipulation, coded as 1 or -1 ("antidepressant" infusion cue or calibration no-infusion cue, respectively) and the reinforcement manipulation, coded as 1 or -1 (positive or baseline sham neurofeedback, respectively). The expectancy manipulation regressor was aligned to the infusion event and the expectancy ratings event, whereas the reinforcement manipulation event was aligned to the neurofeedback event and the mood ratings event. For all models we convolved boxcar regressors with the HRF and used general linear models using FSL FEAT for each run and participant.

Group Level Statistical Analysis. We conducted group level voxel-wise analyses using randomize in FSL. We used threshold-free cluster enhancement to determine significant clusters ($1-p > 0.05$). For each contrast we conducted one-sample t-tests during the placebo session only. We then conducted paired samples t-test for each contrast (Placebo > Naltrexone and Naltrexone > Placebo).

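### The neurofeedback task has two stated group-level analyses, with different covariates and different whole-brain corrections, and nothing says which governs

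*Combined protocol and SAP*

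**What the plan says.** The Research design text of the proposal part is in the future tense and concerns intravenous naloxone against saline. It states that "a random effects analysis will determine the main effects of the valance (positive versus negative neurofeedback"). The resulting maps are to be "thresholded with height and extent values generated by Monte Carlo simulations with 3dClustSim", with overall type I error held at p < 0.05. To deal with confounding, "sex and depression severity will be entered as covariates in statistical models". The same paragraph then plans to extract the mean rACC signal and regress it on variables of interest, which is the analysis that AIM 2 needs.

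The section Group Level Statistical Analysis is in the past tense and concerns oral naltrexone against placebo. It says: "We conducted group level voxel-wise analyses using randomize in FSL". On correction: "We used threshold-free cluster enhancement to determine significant clusters", with the cut-off printed as 1-p > 0.05. On the tests: "For each contrast we conducted one-sample t-tests during the placebo session only". Paired t-tests of placebo against naltrexone, in both directions, follow. No covariate is named.

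Neither section mentions the other's model or correction, and no text says that one replaces the other. How sex and severity are coded, whether they are centred, when severity is measured and which tests carry them are all left open.

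**The concern.** Both sections describe the whole-brain group analysis of the neurofeedback task, and both cannot be followed. One has covariates and a simulation-based cluster threshold. The other has plain t-tests and a permutation-based threshold. A reader who finds a significant cluster, or none, cannot tell which rule was fixed in advance.

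The error rate of 0.05 belongs to one rule applied once. If the model and the correction may be picked with the maps in view, that rate is no longer assured. The stated reason for the covariates is confounding, which does not apply equally to every test in the plan, so the reader also cannot work out where they were meant to go.

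**Working it through.** **1. The two descriptions side by side.**

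| Item | Research design | Group Level Statistical Analysis |
|---|---|---|
| Effect tested | positive vs negative neurofeedback; no drug contrast named | each first-level contrast (for this task, positive vs baseline sham feedback): placebo session alone, then placebo vs naltrexone |
| Model | random effects, with sex and severity | one-sample and paired t-tests, no covariate named |
| Correction | 3dClustSim, overall p < 0.05; no cluster-forming height given | permutation TFCE, printed as 1-p > 0.05 |

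Two covariate sets × two corrections = 4 combinations if the sections are mixed.

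**2. Sample sizes.** The plan recruits 20 and gives no power calculation to reproduce. The participant counts agree: 25 - 2 - 3 = 20 for the neurofeedback task in both sessions. For the contextual framing task there are 20 placebo sessions and 20 - 3 = 17 pairs.

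**3. Do the covariates matter for the paired drug contrast?** In a crossover, whatever is constant within a patient cancels from that patient's placebo-minus-naltrexone difference. A paired model with one column per patient has 1 + 20 = 21 columns and rank 21. Adding sex and severity gives 23 columns and still rank 21. In a simulated data set the drug estimate was -0.0693 both ways. So sex, and severity if measured once at baseline, cannot confound this contrast. If severity were scored at each session, 7-10 days apart, the argument would not cover it.

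**4. Cost of centred covariates.** In a one-sample or difference-score model, mean-centred covariates leave the intercept equal to the plain mean (0.6898 both ways in a test draw). Two covariates cost 2 degrees of freedom. I took the effect that gives 80% power without covariates and assumed that the covariates explain no variance:
- n = 20, effect 0.66 SD: df 19 to 17, power 80% to 79.5%.
- n = 17, effect 0.724 SD: df 16 to 14, power 80% to 79.2%.

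**5. Conditional note: uncentred severity.** In the same kind of model with severity uncentred, the intercept is the effect at Hamilton 0, while entry requires a score above 14. With severity as the only covariate, the standard error grows by

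sqrt(1 + n/(n-1) × (mean/SD)²).

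The documents give no Hamilton mean or SD, so these are assumptions (n = 20):
- mean 16, SD 6: sqrt(1 + 20/19 × 7.11) = 2.9
- mean 20, SD 4: sqrt(1 + 20/19 × 25) = 5.2
- mean 22, SD 2: sqrt(1 + 20/19 × 121) = 11.3

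If the effect does not vary with severity, power at 0.66 SD falls from 80% to about 6-16% over means of 16-22 and SDs of 2-6. If it changes by 0.05 SD per point and is 0.66 at Hamilton 20, the intercept becomes 0.66 - 20 × 0.05 = -0.34, or 0.66 + 20 × 0.05 = 1.66 for the opposite slope.

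**6. The printed TFCE cut-off.** 1-p > 0.05 is the same as p < 0.95. A corrected p < 0.05 is 1-p > 1 - 0.05 = 0.95.

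**The case against.** The best reply is that only one description is live. Research design belongs to the naloxone proposal and an earlier form of the task. Group Level Statistical Analysis reports the naltrexone study as conducted, so the second simply supersedes the first. That is plausible, and it means that both being in force is not shown. But no text retires the proposal part, and the later text still leans on it: the section on the Antidepressant Placebo fMRI Task sends the reader to a figure in the study protocol. The proposal part is also the only place that plans the rACC regression and the only one that prints a usable error rate. The missing statement of precedence therefore stands.

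That the later section has no covariates is inferred from its silence, though plain t-tests make this the natural reading.

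Three stronger readings are tempting and are not supported:
- **The drug test would estimate an effect at Hamilton 0, with almost no power.** Research design does not say that severity enters uncentred and does not tie the covariates to a drug contrast. In a paired model with patient columns they drop out. Step 5 is a warning about one possible coding.
- **The later section removes adjustment from AIM 2.** That section covers voxel-wise tests and does not describe the AIM 2 regression. The covariate sentence in Research design stands shortly before the rACC regression and plausibly covers it.
- **The drug result turns on which section is followed.** For covariates this is not shown: none, or centred ones, give 80% against 79.5% power.

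**Conclusion.** The contradiction holds. For the neurofeedback task the document states two covariate sets and two whole-brain corrections without saying which governs, so both could be chosen after the maps are seen. Nothing shows that this happened. Its effect on the error rate cannot be computed, because the agreement between the two corrections on these data is unknown.

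The TFCE cut-off is misprinted, and needs correcting if that rule is kept. Taken literally it conflicts with the 0.05 rate in the proposal part.

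The covariates' coding, timing and target tests are a specification gap and not a demonstrated error. The standard error inflation of roughly 3 to 11 times applies only to uncentred severity in a one-sample or difference-score model, under assumed Hamilton means and SDs. That sex and severity are unnecessary in the paired contrast assumes that severity is measured once. This should be corrected, but it does not by itself invalidate the drug comparison.

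**What to change.** State one governing group model and one multiplicity rule:

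- **Correction.** For example, make permutation TFCE the only whole-brain rule, delete 3dClustSim, and print the threshold as corrected p < 0.05 (1-p > 0.95). Which method is kept is a matter of preference; that there is only one is not.
- **Paired drug contrast.** No sex or severity covariate. State that severity is the single baseline measurement, if that is so.
- **One-sample models.** Say whether they carry sex and severity. If they do, mean-centre both on the patients in that analysis: 20 for the placebo session, or 17 if a contextual framing analysis is limited to patients with both sessions.
- **AIM 2.** State explicitly that the between-patient regression of mood improvement on rACC signal keeps the adjustment for sex and severity that Research design implies.
- **Dating.** Because the later section reports work already done, date the clarification and say which model and correction were run. New wording cannot make a past choice prospective.

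The cost is text, plus up to 2 degrees of freedom where centred covariates are kept. If the analysis that was run differs from the one chosen here, it also means a rerun or a stated deviation.

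### Contextual framing task: with one contrast per regressor, the context-type map covers neutral faces only, and the two interaction terms are differences from neutral

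*Combined protocol and SAP*

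**What the plan says.** The model is described under MRI Analysis, in the subsection on first-level analysis of the contextual framing task. Emotion is one linear term (happy 1, neutral 0, fearful -1). For context: "Similarly, the context regressor was coded as 1 for pleasant and -1 for unpleasant context". Two further regressors follow: "The interaction term included two regressors, one for the effect of context on happy faces" and "another one for the effect of context on fearful faces". Each is 1 for pleasant and -1 for unpleasant context within its face type and 0 elsewhere. A nuisance trial regressor completes the set.

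All regressors share the same timing: "We aligned the boxcar regressors with trial onset (length = trial duration". They are then convolved with the haemodynamic response, and the fit is made by run: "We then used the resulting time-series to regress against BOLD signal for each run and participant". On contrasts, the text says the analysts "constructed contrasts for each regressor (i.e., emotion, context type, emotion x context type interaction". It gives no contrast weights, no orthogonalisation and no separate models.

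Under Group Level Statistical Analysis, every contrast goes to a one-sample test in the placebo session and to paired tests of placebo against naltrexone in both directions.

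**The concern.** A context regressor coded +1/-1 on all trials measures the overall context effect only while no other regressor carries context. Here two others do, one for happy and one for fearful faces. Together they absorb whatever is specific to those faces and leave the all-trials regressor to be estimated from neutral faces. A contrast on that regressor alone therefore does not match its name.

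The two interaction terms have a related problem. The text describes them as context effects within happy and within fearful faces, but in this model they are departures from the neutral-face effect.

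Context is the manipulation in this task. A naltrexone effect reported on context could rest on one third of the trials. An empty interaction map could be misread as no naltrexone effect on context in happy or fearful faces. The final sample is 20 placebo and 17 naltrexone sessions, so there is little data to spare.

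**Working it through.** The plan states no figure on this point, so there is none to reproduce. The check is of what each coefficient estimates.

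**Inputs.** Regressor coding is from the first-level section. The task section gives 144 trials per visit with the three face types equally frequent, hence 48 per face. MRI Data Acquisition gives two runs. Assumed, because not stated: 24 trials in each face-by-context cell, and 72 trials per run with 12 per cell.

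**What each coefficient estimates.** Let t, e, b_c, b_h and b_f be the coefficients for trial, emotion, context, context-in-happy and context-in-fearful. The cell means (pleasant +, unpleasant -) are:

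- happy: t + e ± (b_c + b_h)
- neutral: t ± b_c
- fearful: t - e ± (b_c + b_f)

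Let d be half the pleasant-minus-unpleasant difference for a face type. Then b_c = d_neutral, b_h = d_happy - d_neutral and b_f = d_fearful - d_neutral. The design has full column rank (5). With balanced cells, the least-squares weights are:

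| Coefficient | happy P, U | neutral P, U | fearful P, U |
|---|---|---|---|
| context | 0, 0 | 0.5, -0.5 | 0, 0 |
| context-in-happy | 0.5, -0.5 | -0.5, 0.5 | 0, 0 |
| context-in-fearful | 0, 0 | -0.5, 0.5 | 0.5, -0.5 |

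Three patterns of (d_happy, d_neutral, d_fearful) show the consequence:

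- (1,1,1) gives b_c = 1 and b_h = b_f = 0. Both interaction terms vanish although context acts fully on happy and fearful faces.
- (1,0,1) gives b_c = 0 and b_h = b_f = 1. The context contrast is zero although the average effect is 2/3.
- (0,1,0) gives b_c = 1 and b_h = b_f = -1. Both interaction terms are non-zero although context does nothing to happy or fearful faces.

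Convolution is linear and all regressors share the same timing, so the algebra carries over. Convolved runs with unbalanced cells returned the same coefficients. If cells are unbalanced and the emotion effect is not linear, estimates move slightly: by at most about 0.08 per unit of quadratic effect with cells of 28/20, 22/26 and 22/26.

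**First-level precision.** With independent errors of variance σ²:

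- b_c alone: (1/4)(σ²/24 + σ²/24) = σ²/48
- average, b_c + (b_h + b_f)/3: (1/9)(3 × σ²/48) = σ²/144
- ratio: 144/48 = 3.0 in variance, √3 = 1.73 in standard error

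Per run the variances are σ²/24 and σ²/72, with the same ratio. A per-run simulation (72 trials, 5 s trial-long boxcars, intervals of 2 to 6 s, TR 1 s, 0.008 Hz high-pass, 100 random orders) gave a mean variance ratio of 2.97 (95% range 2.54 to 3.33).

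**Group-level precision.** Let r be the between-subject variance divided by the first-level variance of the averaged effect, assumed equal for both contrasts. The standard-error ratio is √((r+3)/(r+1)): 1.41, 1.29, 1.15 and 1.09 at r = 1, 2, 5 and 10. The documents do not give r.

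**Shift in target.** Each trial shows a "contextual image for 2 seconds (Context phase) followed by the rating of the valence of an ambiguous emotional expression for 3 seconds". The simulated signal had a context response of size k in the first 2 s, the same for all faces, and a face-dependent response in the last 3 s. Entries are b_c as a percentage of the average context effect:

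| Face-phase effect (happy, neutral, fearful) | k = 0.5 | k = 1 | k = 2 | k = 5 |
|---|---|---|---|---|
| (1, 1, 1) | 100 | 100 | 100 | 100 |
| (1, 0.5, 1) | 71 | 77 | 84 | 92 |
| (0.5, 1, 0.5) | 134 | 126 | 117 | 109 |
| (1, 0, 1) | 32 | 49 | 66 | 83 |
| (0, 1, 0) | 202 | 169 | 141 | 119 |

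The last two rows are extremes. The error runs in either direction. The bare coefficient has the larger expected t only where its ratio to the average exceeds the standard-error ratio.

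**The case against.** The sentence on contrasts names three effects for four regressors, so it may be shorthand, and weights could have been applied that the text does not report. On that view the context-type point is a reporting gap. This stands as a limit: the point holds only if one contrast per regressor is meant. That is nevertheless the literal wording, and nothing else in the documents changes it.

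The second half could be called loose wording, since the coding is printed and the terms are valid interaction terms under a correct heading. But the description would fit only if the all-trials context regressor were left out or separate models were fitted, and neither is described. A reader relying on it would misread both a null and a positive map.

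The practical harm is also open to question. The task has no stated hypothesis and lies outside Aims 1 to 3, no text requires an equal-weight average, and the group-level loss is unknown. The face manipulation is mild too ("we merged morphed only 20% of happy or fearful face to with the neutral face"), so similar context effects across faces are plausible, and the cost is then mainly precision. All of this stands and limits how serious the point is. It does not make the label right.

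**Conclusion.** The concern holds. Read as written, the context-type map is the context effect on neutral faces, from 48 of 144 trials. Separately, whenever all four regressors share one model, the two interaction coefficients are happy minus neutral and fearful minus neutral, not effects within those faces.

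The loss at first level is a factor of 3.0 in variance and 1.73 in standard error, given equal cells. At group level it is smaller and cannot be computed from the documents, so no loss of power is claimed. The size of any shift in target depends on how far context effects differ between faces, and its direction is unknown.

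The emotion contrast and the antidepressant placebo task are unaffected. This should be fixed, but it does not touch the stated aims.

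**What to change.** Keep the regressors and change the contrasts:

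- Define context type as context + 1/3 context-in-happy + 1/3 context-in-fearful, and take that contrast to the one-sample and paired group tests.
- Relabel the two interaction terms as context, happy minus neutral, and context, fearful minus neutral. Carry them as two signed contrasts rather than a first-level F, because the planned group tests are t-tests.
- If the bare context coefficient is reported, label it as context in neutral faces.
- If within-face effects are wanted, use context + context-in-happy and context + context-in-fearful, and count them as extra tests.
- If combined weights were in fact used, state them.

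The cost is one contrast vector recomputed for each run, two labels, and a rerun of the group step for this task. The model is full rank, so no refit and no new data are needed. The group maps number 4 contrasts × (1 one-sample + 2 directional paired) = 12, the same as one contrast per regressor. If only the three named effects were planned, the starting count is 3 × 3 = 9 and the fix adds 3. Each optional within-face effect, including the neutral one, adds 3 more.
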